The Audéo P is a hearing aid on the Paradise platform and is worn with the processor behind the ear with the receiver in the ear canal. The microphone(s) pick(s) up sound waves, convert(s) them into an electrical signal which is sent to the Digital Signal Processor (DSP), which is part of the hybrid. The DSP applies the amplification to the electrical signal, which means that the amplitude of the signal gets modified. The modified electrical signal is forwarded to the external receiver, which is held in the ear canal with the aid of an earpiece. The external receiver converts the electrical signal into an acoustic signal and submits it to the ear drum. An integrated Bluetooth antenna enables the hearing aid to also receive digital signals (e.g. streamed music), which will be processed in the same way.

The overall intended purpose of the device is to amplify and transmit sound of the ear and thereby compensate for impaired hearing.

4 Design of the clinical investigation

This investigation is a single-center, randomized, double-blinded crossover study with two treatment conditions. Treatment conditions include an OTC device condition, wherein the participant believes they are wearing an OTC device, and a prescriptive device condition, wherein the participant believes they are wearing a hearing aid that has been programmed prescriptively for their hearing loss. There will be two arms of the study; one group of participants will be new users, who have never worn or owned a hearing aid, and the other group will consist of experienced hearing aid users, defined as having worn hearing aids for at least six months.

During the investigation, the participants will be told which condition they are in because the aim of this investigation is to measure bias. That being said, the investigators will use pre-planned scripts when conversing with the participants in the study to ensure that factors relating to the bias are equitable for the participants, notwithstanding the bias the participants may or may not have prior to the study appointment. The QuickSiN test will be scored by a sub-investigator who will be blinded to the condition in order to minimize tester bias. Because this investigation follows a cross-over design, participants will be randomly assigned to one of two possible orders for exposure to the two treatment arms to counteract potential order effects.

5 Risks and benefits of the investigational device and clinical investigation

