An a priori power analysis was conducted in G*Power3 for the primary objective. The primary objective will be measured for two groups (experienced and inexperienced) via repeated measures of the QuickSiN for two conditions (OTC and prescriptive). A repeated measures, within and between factors ANOVA, using a medium effect size ($f = .55$) and alpha of .05, would require a sample of 14 participants per group (inexperienced and experienced) for a total of 28 participants to achieve a power of .95.

Speech-in-noise (i.e. QuickSiN) data for the primary objective from all subjects will be analyzed. Participants will be grouped by hearing aid experience (either inexperienced or experienced) as a part of these analyses. For the primary objective and its associated endpoint (QuickSiN benefit), two lists will be presented for each condition in order to expect a 1.8 dB critical difference between the conditions with a 80% confidence level. The principal investigator will conduct the analysis of the primary endpoint after data has been collected from all participants for all test conditions.

10 Investigation Duration

This investigation is scheduled to last approximately 10 weeks. Each participant's duration will be one day of testing.

11 Data handling and management

Electronic or paper based CRFs will be used to capture the participant data. If electronic, subjective questionnaires will be available in the EDC system and the participant will be able to read question and choose answer. If paper based subjective questionnaires are used, the participant will answer each question and the results will be transferred to the EDC by the investigator. Objective data will either be entered in directly to the EDC system, or transferred from a paper based CRF into the EDC system.

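### The plan randomises label order but does not say how QuickSiN lists are balanced against label, and the model it names has no period or list term

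*Combined protocol and SAP*

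**What the plan says.** Section 4 describes a "single-center, randomized, double-blinded crossover study with two treatment conditions". It states that "participants will be randomly assigned to one of two possible orders for exposure to the two treatment arms to counteract potential order effects". It gives no randomisation method and does not promise equal numbers per order.

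Section 9 gives the only rule on test lists: "two lists will be presented for each condition". The stated reason is to "expect a 1.8 dB critical difference between the conditions with a 80% confidence level". No section names the lists, says that the four presentations use different lists, or says how lists are allocated to label or to test position.

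The only model named is in the power paragraph of Section 9: "A repeated measures, within and between factors ANOVA", with experience group as the between factor and label as the within factor. No period, order or list term is mentioned there or in the analysis paragraph that follows.

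Section 10 puts both conditions close together: "Each participant's duration will be one day of testing". Sections 4 and 8 require the scorer to be blinded to condition.

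**The concern.** The label is the only thing that is meant to differ between the two conditions. Any other systematic difference between them will be read as a placebo effect. The material on which the score is obtained is an obvious candidate, because each condition is scored on only two lists.

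Randomising label order balances label against test position. It does not balance label against list. If lists are prepared per condition, a participant who hears OTC second still hears the OTC lists, and list pair cannot be separated from label. No analysis of the resulting data could undo that, a larger sample would not shrink it, and blinded scoring does not address it.

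If lists are instead attached to test position, or the same lists are heard twice in a day, the difference is between periods. That matters less, but the named model leaves it in the error term.

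**Working it through.** **Inputs from the documents.** N = 15 + 15 = 30 (Sections 7 and 8). Two lists per condition, 1.8 dB critical difference at 80% confidence, and alpha 0.05 (Section 9). Two label orders (Section 4).

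**Inputs assumed.** The documents give no difference in difficulty between list pairs (b), no period effect and no SD of the within-person difference. I take b = 0.25, 0.5 and 1.0 dB. For the SD I use two readings of the plan's 1.8 dB and one larger value:

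- two-sided 80% limit: 1.8 / 1.2816 = 1.40 dB
- one-sided 80% limit: 1.8 / 0.8416 = 2.14 dB
- 2.5 dB, to allow for variation between people in their response to the label. The first two values describe test error only.

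The 1.8 dB figure is taken as given, since the documents do not contain what is needed to derive it.

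**Case 1: a list pair is tied to a label.** Each participant's label difference is the true label effect plus b plus error, so the bias is b in full. With no true effect, the label test follows a noncentral t with 30 − 2 = 28 df and noncentrality b / (SD/√30). For b = 0.5 dB and SD 1.40 dB, the SE is 1.4045/√30 = 0.256 dB and the noncentrality is 0.5/0.256 = 1.95. Two-sided rejection probabilities at alpha 0.05 are:

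| SD (dB) | SE (dB) | b = 0.25 | b = 0.5 | b = 1.0 |
|---|---|---|---|---|
| 1.40 | 0.256 | 0.156 | 0.469 | 0.964 |
| 2.14 | 0.390 | 0.095 | 0.235 | 0.696 |
| 2.5 | 0.456 | 0.083 | 0.185 | 0.562 |

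**Case 2: lists run in a fixed sequence, or are repeated.** The difference now goes with test position. Code g = +1 for one label order and −1 for the other. The label difference is the true effect plus b·g plus error, and the bias is b(n₁ − n₂)/30.

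- *Order split 15/15.* The bias is 0. With no period term, b stays in the error, and at b = 1.0 dB the SD rises from 1.40 to about √(1.4045² + 1.0²) = 1.72 dB. By simulation with SD 1.40 dB, the false-positive rate is about 0.038 at b = 0.5 dB and about 0.017 at b = 1.0 dB, both below the nominal 0.05. At b = 1.0 dB, power for an assumed true label effect of 0.75 dB is 0.66, against 0.81 with no period effect. A period term restores both the 0.05 and the 0.81.
- *Simple randomisation.* Averaged over possible allocations, the bias is 0 and the false-positive rate is about 0.050.
- *Order split 20/10.* The bias is b(20 − 10)/30 = b/3. At b = 0.5 dB this is 0.17 dB, with a false-positive rate of about 0.08. At b = 1.0 dB it is 0.33 dB, with a rate of about 0.13.

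**What a model term can and cannot repair.** In Case 2 a period term removes the problem, because list pair and period coincide. In Case 1 a list term would coincide with label, so the allocation itself has to change.

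**The case against.** The strongest reply is that the plan is silent on list allocation, and silence is not a statement that lists are fixed to labels. Playing lists in a set sequence fits the text equally well and gives no systematic bias. Fixing lists to labels would also sit badly with the plan's own blinding, because a scorer could learn the condition from the list. All of this stands, although the blinding requirement does not establish that lists are rotated.

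A reader might infer that the plan leaves list pairs unrotated, so that 47% is this trial's false-positive rate. The documents support neither step. The figure holds only if a pair is tied to a label, the pairs differ by 0.5 dB and the SD is 1.40 dB. At larger SDs the rate is roughly half that or less.

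A reader might also infer that hearing a list twice could pass for a label effect. A repeated list favours whichever condition comes second, and the randomised order spreads that gain over both labels on average. It reaches the label contrast only through an unequal order split, and then only in part.

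The reply does not remove the gap. The text permits the harmful allocation, and the named model would not absorb even the milder one.

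**Conclusion.** The point holds as a gap in the design and the model, not as a demonstrated bias. The plan does not ensure that list pairs are balanced against label, does not require four different lists, and names no period or list term.

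The consequence depends on an allocation rule that the plan does not give. Tied to label, a 0.5 dB pair difference raises the false-positive rate from 5% to between about 19% and 47% over the SDs considered. Tied to test position with an even order split, there is no bias, but the test becomes conservative and loses power. With an uneven split, a fraction of the period difference reaches the label contrast. The list difference, the period effect, the SDs and the 0.75 dB label effect are all assumptions. The sizes therefore show what could happen and are not estimates for this trial.

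The change is worth making because it removes the harmful case by design and recovers precision in the other, at almost no cost.

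**What to change.** In Section 4, name four different lists, grouped as pair A and pair B, and state that no participant hears a list twice. Within each experience group, randomise to four sequences: OTC first or Prescriptive first, crossed with A then B or B then A. Record on the case report form which lists were used in which condition and position.

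In Section 9, add period and list pair to the group-by-condition model. With the four sequences, label, period and list pair can all be estimated separately.

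The cost is a randomisation list with four sequences instead of two, and two extra model terms. Fifteen per group cannot divide evenly by four, so each group splits 4/4/4/3. The period and list terms handle that imbalance. The number of lists played and the sample size stay the same. If the team already rotates lists in this way, a sentence in Section 4 and the two model terms in Section 9 are enough.
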